4.3.3. Fixed Dosing Approach

A fixed-dose approach will be applied for the FIH study of PF-07260437 given that fixed dosing approach was shown to provide similar PK variability compared to a body-weight adjusted dosing for monoclonal antibodies, therapeutic peptides, and proteins ([Wang et al,](#)

2009; Zhang et al, 2012; Hendrikx et al, 2017). In addition, fixed dosing offers ease of preparation and less chance of dosing errors.

4.3.4. Dosing Interval (Q2W)

The Q2W dosing frequency of PF-07260437 in this study was selected based on the projected $t_{1/2}$ of 15 days in humans. Based on emerging PK, PD, and safety data, regimens with alternative dosing frequencies (eg, weekly administration, or Q4W) may also be considered.

4.3.5. Criteria for Dose Escalation

BLRM guided by the EWOC principle will be used in dose escalation. See Table 8 and [Appendix 9](#) for more details on the model. Using DLT data at all tested dose levels and prespecified prior distribution of model parameters, posterior probabilities of probability of having a DLT falling into 3 dosing intervals (underdosing, target dosing, overdosing) will be calculated for all dose levels. A dose may only be used for newly enrolled participants if the risk of excessive toxicity, ie, toxicity higher than 0.33 at that dose is less than 25%.

Typically, participants will be enrolled in cohorts of approximately 3 participants with at least 1 DLT evaluable participant in the first dose level in Part 1 without a priming dose and 2 DLT evaluable participants at all other dose levels in Part 1 with or without a priming dose. The maximum dose increases from the previous dose levels for regimen will be up to 200% (dose tripling from the previous dose level) but will be adjusted to no more than 100% (dose doubling from the previous dose level) following the observation of a DLT or if there are two Grade ≥ 2 clinically significant treatment-related AEs.

The provisional dose levels to be evaluated are listed in Table 8.

Table 8. Provisional Dose Levels in Dose-Escalation (SC Administration)

Dose Level ^a	Dose (μg)
-1 (if applicable)	60
1 ^b	100
2	300
3	900
≥ 4	Escalation to continue to MTD or desired pharmacologic activity

a. Intermediate doses may be evaluated based on clinical findings. Maximum 3-fold increment (dose tripling) at each dose level.
b. If the 100 μg SC Q2W dose is not tolerated, then a lower dose of 60 μg Q2W via SC route will be evaluated.

Dose escalation will stop when stopping criteria are met (see [Appendix 9](#)). According to the stopping criteria, at least 6 participants will be evaluated at the MTD.

Intra-participant dose escalation to the next dose level may be considered in consultation with the sponsor for participants(s) enrolled in the first dose level with the following conditions: 1) have cleared the DLT period in the dose escalation phase, 2) the next immediate higher dose level is safe in all participants with no DLTs, and 3) a period of a minimum of 2 cycles after the DLT observation period with the next immediate higher dose level has confirmed there are no clinically significant toxicities.

Stopping criteria:

The sponsor estimates that the maximum number of participants in the Part 1 dose escalation portion of the trial is 40 participants. However, the actual number may be more or less based on observed PK and safety. The dose escalation will stop when the following criteria are met:

- At least 6 participants have been treated at the recommended MTD or RDE.
- The dose d for PF-07260437 satisfies 1 of the following conditions for the mono-escalation part:
 - The probability of target toxicity at dose d exceeds 50%, ie, $\Pr(\text{ind} < 0.33) \geq 50\%$, or
 - A minimum of 15 participants have been treated in Part 1.

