4.3.1.2. Alternative Intravenous Administration

If PK and safety data suggest that SC route is not a viable approach (eg, very low SC bioavailability or intolerable ISR), IV administration may also be evaluated in subsequent dose cohorts. To provide sufficient safety margin, the IV starting dose will be 20% of the highest safe/tolerable SC dose with assumption of 2.5 L of plasma volume for IV administration. For example, if the 300 µg SC dose level is deemed tolerable, the IV starting dose will be 60 µg. Notably, in the absence of any clinical safety data from SC dosing, the MABEL approach would yield an IV starting dose of 23 µg as the predicted C_{max} is similar to the EC₅₀ value from the most sensitive in vitro assay (0.062 nM). While it is not feasible to administer this IV dose of 23 µg based on the current formulation (with a lowest feasible IV dose of 45 µg), the IV route will not be potentially implemented until a SC dose level of \geq 300 µg. Therefore, the lowest possible IV dose is 60 µg, which is expected to provide similar exposure coverage with 300 µg at SC dose level 2 (see [Table 8](#)).

In addition, the HNSTD was 0.1 mg/kg/week from the IV arm of the GLP 1-month toxicity study in cynomolgus monkeys. This yielded an IV starting dose of 376 µg (1/6 HNSTD assuming 70 kg body weight in humans), which is higher than our provisional IV starting dose of 60 µg.

If IV route is evaluated, inpatient monitoring in a hospital for at least 48 hours after the first dose in Cycle 1 in dose escalation will be implemented as described in [Section 6.1](#). Additional inpatient observation for subsequent cycles beyond Cycle 1 may be considered based on the investigator's discretion and should be discussed with the sponsor.

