9.3.2. Primary Endpoints/Estimands/Analysis

Part 1

Determination of MTD will be performed using Per-protocol analysis set (evaluable for MTD). The dose escalation in Part 1 of the study will be guided by a Bayesian analysis of DLT data for PF-07260437. Dose toxicity is modelled using 2-parameter logistic regression for the probability of a participant experiencing a DLT at the given dose for the monotherapy and using BLRM model specifically developed for combinations separately for regimens with and without priming. A mixture of weakly informative prior distribution based on nonclinical/expert opinion information and a MAP prior based on historical data will be used to define the prior distribution for the PF-07260437 monotherapy dose escalation. The MAP prior for the logistic model parameters for this study is the conditional distribution of the parameters given the historical data.

After each cohort of participants, the posterior distribution for the risk of DLT for new participants at different doses of interest for PF-07260437 will be evaluated separately for cohorts with and without priming, taking into account the different DLT observation periods (28 days for the regimen without priming; priming doses plus 2 full doses for the regimen with priming). The posterior distributions will be summarized to provide the posterior probability that the risk of DLT lies within the following intervals:

Under-dosing:	[0, 0.16]
Targeted dosing:	[0.16, 0.33]
Overdosing:	[0.33, 1]

Dosing decisions are guided by the EWOC principal (Rogatko et al, 2007). A dose may only be used for newly enrolled participants if the risk of overdosing at that dose is less than 25%.

Recommendation from the BLRM, along with safety (AEs, SAEs), laboratory, PK, biomarker, and other relevant data, will be used at the time of each dose escalation and for MTD/RDE determination.

Prior distributions:

Weakly informative prior distributions based on pre-clinical/expert opinion information will be chosen for the logistic parameters for prior distribution in Part 1, see [Appendix 9](#).

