10.9.1. Statistical Model

Let $\pi(d)$ be the risk of DLT for PF-07260437 given as a single agent at dose d . The dose-DLT model is logistic:

$$\text{logit}(\pi(d)) = \log(\alpha) + \beta \log\left(\frac{d}{d^*}\right)$$

The parameter d^* is the reference dose in the model and is used to scale the doses of PF-07260437. The $\alpha, \beta > 0$ are the parameters of the model such that $\alpha (>0)$ is the PF-07260437 odds of a DLT at d^* ; and $\beta (>0)$ is the increase in the log-odds of a DLT by a unit increase in log-dose.

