### Part 1 Dose Escalation

Participants will receive escalating doses of PF-07260437 administered as SC injection with a starting dose level of 100 µg Q2W as monotherapy. Additional dosing frequency such as Q1W or Q3W may be considered if supported by emerging clinical PK, PD, and safety data. BLRM guided by EWOC principle will be used to guide the dose escalation process and determine the MTD/RDE. The maximum allowable PF-07260437 dose increment is 200% (dose tripling from the previous dose level) for cohorts but will be adjusted to no more than 100% (dose doubling from the previous dose level) following the observation of a DLT or if there are two Grade  $\geq 2$  clinically significant treatment-related AEs. For monotherapy without priming strategy, DLT will be assessed during the first 28 days. For monotherapy with priming, the DLT assessment period will extend to include priming doses plus 2 full doses (eg, first 42 days). Each dose level group will include approximately 3 participants, with at least 1 DLT evaluable participant per cohort in the first 2 cohorts and at least 2 DLT evaluable participants per dose level group in the remaining cohorts for Part 1. Per BLRM design, expanding additional participants at lower dose levels are allowed to assess safety. Dose escalation cohorts may be switched from SC administration to IV administration if SC administration is not considered as the preferred route due to severe skin toxicities, low PK exposure or other reasons. IV administration cohorts may initiate at a dose level that is no greater than 20% of the highest SC dose level that is deemed tolerable (eg, starting at 60 µg IV Q2W if 300 µg SC Q2W is deemed tolerable) depending on emerging PK and safety data.

A priming dose approach in the next dose level may be initiated if a dose level induces  $\geq$  Grade 2 CRS (lasting for  $>24$  hours) occurs in  $>1$  participant despite treatment with tocilizumab and/or vasopressors. If the dose escalation has reached the MTD and a priming dose has not been previously incorporated to the dose regimen, a priming dose escalation cohort to minimize  $C_{max}$  may be initiated based on clinical safety, PK/PD, and clinical efficacy.

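### As written, the dose-escalation model has no term for route, so after a switch from SC to IV the EWOC limit would be computed on nominal micrograms and could understate IV overdose risk

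*Protocol*

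**What the plan says.** Protocol Section 10.9.1 (Appendix 9) models the "risk of DLT for PF-07260437 given as a single agent at dose" d as logit π(d) = log(α) + β·log(d/d*), where d* "is the reference dose in the model and is used to scale the doses of PF-07260437". There is no route term. Section 10.9.2 gives the prior in terms of an anticipated DLT rate p* at d*; neither p* nor d* has a stated value.

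Section 4.3.5 fits the model "Using DLT data at all tested dose levels and prespecified prior distribution of model parameters" and opens a dose to new participants only if the risk of "toxicity higher than 0.33 at that dose is less than 25"%. Its dose grid, Table 8, is for SC only.

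Section 9.3.2 names one split: the posterior "will be evaluated separately for cohorts with and without priming". SAP Section 2.2 repeats it. Section 4.1 gives SC and IV dosing without priming the same 28-day DLT window, directly before it introduces the BLRM.

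The IV route is provided for. SAP Section 2.2 says "Dose escalation cohorts may be switched from SC administration to IV administration", and Protocol Section 4.3.1.2 says "the IV starting dose will be 20% of the highest safe/tolerable SC dose". No IV prior, model or dose grid follows. On frequency, Section 4.3.4 adds that "regimens with alternative dosing frequencies (eg, weekly administration, or Q4W) may also be considered".

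**The concern.** A statistician who runs the model from this text, with a mix of SC and IV cohorts and no priming, has one data set and one dose axis. IV 540 µg would then count as a lower dose than SC 900 µg, and DLT-free SC participants at 900 µg would count as evidence that IV 540 µg is safe. Sections 4.1 and 4.3.1.1 link Cmax to CRS and say that the SC route blunts it, and Grade 3 or higher CRS is a DLT. On the protocol's reasoning, a microgram given IV is not interchangeable with a microgram given SC for the event being modelled.

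At stake is the EWOC limit, which is the quantitative safety gate for new participants, and through it the MTD. IV DLTs entered at their nominal dose would also distort the curve fitted to the SC doses.

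**Working it through.** **1. The protocol's SC-to-IV figures.**
- IV start by the 20% rule: 0.20 × 300 = 60 µg, as stated; ratio 300/60 = 5.
- IV MABEL dose: 9.2 ng/mL ÷ 0.063 nM implies about 146 kDa. Then 0.062 nM × 2.5 L × 146 kDa = 22.6 µg, which rounds to the stated 23 µg; ratio 100/23 = 4.35.
- Cmax check: 60 µg ÷ 2.5 L = 24 ng/mL IV, against 3 × 9.2 = 27.6 ng/mL for 300 µg SC, using the linear PK projected in Section 2.2.2.
- For AUC, the assumed 70% SC bioavailability gives only 1/0.70 = 1.43.

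The documents therefore support a factor of about 4.3 to 5 on Cmax and 1.43 on AUC.

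**2. Model.** I used the Appendix 9 logistic with log(α) ~ N(logit p*, SD 2) and log(β) ~ N(0, SD 1), independent, evaluated on a grid. A dose is blocked when P(π > 0.33 | data) is 0.25 or more. Because p* and d* are not given, I assumed two sets:
- 9 priors: p* 0.10, 0.20, 0.33 by d* 900, 2700, 8100 µg.
- 24 priors: p* 0.15, 0.20, 0.25, 0.30, 0.33 by d* 300, 900, 1000, 2700, 8100 µg, leaving out p* 0.33 with d* 300. That pair fails EWOC at 100 µg, whereas Section 9.3.2 says the starting dose passes.

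**3. Main scenario (assumed DLT data).** SC 0/3 at 100, 300 and 900 µg; IV 0/3 at 180 µg (0.20 × 900); IV 2/3 DLTs at 540 µg (3 × 180, within the step limit because no DLT has yet occurred). The question is whether IV 540 µg stays open. IV doses are multiplied by the factor shown; factor 1 is nominal pooling.

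| IV factor | 9 priors: overdose risk | Blocked | 24 priors: overdose risk | Blocked |
|---|---|---|---|---|
| 1 | 2.7-9.4% | 0/9 | 3.3-13.2% | 0/24 |
| 1.43 | 4.5-21.6% | 0/9 | 5.5-27.3% | 3/24 |
| 3 | 13-70% | 6/9 | 16-70% | 19/24 |
| 4.35 | 21-74% | 8/9 | 25-75% | 23/24 |
| 5 | 24-75% | 8/9 | 29-76% | 24/24 |

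The one prior of the nine that stays under the limit at 5-fold (p* 0.10, d* 8100) gives 24.4%.

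**4. Second scenario, next step up (24 priors).** SC 0/3 at 100 and 300 and 2/4 at 900 µg; IV 0/3 at 60 and 120 µg; next IV dose 240 µg (a doubling). Pooled: 0.4-1.1%, never blocked. At 5-fold: 12-70%, blocked under 19 of 24. None of the priors with d* 8100 blocks it.

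**5. The IV start itself.** After SC 0/3 at 100 and 300 µg, the overdose risk at IV 60 µg is at most 0.2% pooled and 6% at 5-fold. Both clear it under all 24 priors.

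**The case against.** **Pooling is not stated.** A reader might infer that the plan directs SC and IV data to be pooled on nominal dose. It does not. The sentence in Section 4.3.5 does not mention route, and it points to an SC-only table. The hypothetical scenarios and operating characteristics are in a Technical Supplement that is not among the documents. This stands. The text nevertheless offers no other way to enter an IV cohort, and a rule on which the primary Part 1 result depends belongs in the protocol and SAP.

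**The 20% rule.** A reader might take it as a conversion that would block later IV doses. It caps the IV starting dose only, and it already protects the first IV cohort. After that, the step limits and EWOC apply.

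**A starker example.** One could triple the IV dose from 540 µg after 1/6 DLTs at SC 2700 µg. Section 4.3.5 allows no more than doubling after a DLT. With IV 0/3 at 540 µg included and 1080 µg next, the 5-fold scale gives 10-39% and blocks only 3 of 9 priors; at 3-fold it blocks none.

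**Dosing frequency.** A reader might conclude that Q4W participants without a DLT could never be evaluable. Section 4.3.6 asks for all planned doses, and the two-dose clause in Section 9.1.1.1 concerns participants who withdraw before two full doses. The documents do not support that conclusion.

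**The committee.** Section 4.3.8 lets the Dose Level Review Committee weigh PK and all safety data, so it could close a dose that EWOC leaves open. That is a real safeguard. But EWOC is written as a condition that must be met, and a probability on the wrong exposure scale misinforms the committee that uses it.

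**Conclusion.** The concern holds as a defect in the model specification, conditional on IV cohorts opening. Read literally, the BLRM enters IV and SC cohorts on one microgram scale, against the protocol's own exposure figures, and the error runs towards understating IV overdose risk. In the main scenario, EWOC alone leaves a dose open after two of three participants had DLTs there: 3-13% pooled against 24-76% at 5-fold.

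The size is illustrative. It rests on assumed p*, d* and DLT data, and on Cmax as the driver of toxicity. At 3-fold the effect is weaker, and at 1.43-fold it largely disappears. The capped IV starting dose is not affected. IV remains optional, so the effect is possible rather than certain.

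**What to change.** In Protocol Section 9.3.2, Appendix 9 and SAP Section 3.1, state that IV and SC cohorts are not pooled on nominal dose. Either evaluate IV as a separate stratum, as is already done for priming, or add a route term. For a separate stratum, the MAP approach already planned for priming is a ready template: derive the IV prior from the SC data on an exposure-equivalent scale, updated with observed PK. Apply the existing 25% EWOC limit within the IV stratum. Give p*, d*, the IV prior and the operating characteristics for a route switch. State likewise how a change of dosing frequency enters the model.

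The cost is protocol and SAP wording, one more model run per dose decision and possibly slower IV escalation. The change should be in place before any IV cohort opens.

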4.3.6. Dose Limiting Toxicity (DLT) Definition

A participant is classified as DLT evaluable if they either 1) receive all the planned doses of the study intervention and have received all scheduled safety assessments during the DLT observation period or 2) have experienced a DLT. If a participant fails to meet these criteria, they may be replaced. The sole exception to criterion 1) is if the participant has missed a minority of safety assessments due to emergency situations (eg, site accessibility issues, inability to go to an external lab, etc). In such cases, the Dose Level Review Committee may judge the participant evaluable, depending on the abundance of the available data.

DLT observation period: For the purpose of dose escalation, the DLT observation period for SC or IV dosing without priming will be 28 days including laboratory results obtained on the morning of Day 29 in each participant. The DLT period for dosing with priming will extend to include the duration of priming doses and 2 full doses (eg, if a single priming dose is administered 2 weeks prior to the first full dose, the DLT evaluation period will be 42 days (14 days plus 28 days) including laboratory results obtained on the morning of Day 43 (C2D15).

Any of the following treatment-related AEs occurring during the DLT observation period that in the opinion of the investigator cannot be reasonably attributed to the participant's underlying disease, concomitant medications or preexisting conditions are considered DLTs. Severity of AEs will be graded according to CTCAE version 5.0, with the exception of CRS, which will be graded according to the ASTCT CRS Consensus Grading for CRS (Appendix 11). For those events involving a worsening of a baseline abnormality, a DLT must represent a clinically significant (in the opinion of the Investigator after discussion with the sponsor) shift from baseline.

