Serious and nonserious AE monitoring		◀ →													
 See Sections 8.2 and Section 8.3.

Table 1. Study Schedule of Assessments – Part 1 Without Priming

Visit Identifier Abbreviations used in this table may be found in Appendix 17	Screening	Treatment Period										EOT	4-week Follow- up	90-day Follow- up for irAEs	Notes
		Cycle 1 = 28 days					Cycle ≥2 (28 days)								
Study Day	-28 to -1	1	2	3 ^a	8	15 ^a	22	1	C3D8 ^b	15					
Visit Window (days)		±2			±2	±2	±2	±2	±2	±2		±7		±7	
Clinical Safety Laboratory Assessments															
Hematology	X	X	X		X	X	X	X		X	X	X			
Blood chemistry	X	X	X		X	X	X	X		X	X	X			
Coagulation	X	Every 8 weeks from C1D1								X					
Lipase and amylase		X						X			X				
TSH and free T4	X														

- Additional visit window may be allowed after discussion and agreement between investigator and sponsor.
- a. End of inpatient observation (PK, ECG, vital signs).
- b. PK/PD and ECG only.
- See [Section 8.2.4](#).
- See [Appendix 2](#) for a list of Clinical Laboratory tests to be done.
- No need to repeat on C1D1 if screening was performed within 7 prior days. All samples will be collected prior to dosing.
- No need to repeat on C1D1 if screening was performed within 7 prior days.
- TSH WNL for institution; in participants with abnormal TSH, if free T4 is WNL and participant is clinically euthyroid, participant is eligible.

Table 1. Study Schedule of Assessments – Part 1 Without Priming

Visit Identifier Abbreviations used in this table may be found in Appendix 17	Screening	Treatment Period										EOT	4-week Follow- up	90-day Follow- up for irAEs	Notes
		Cycle 1 = 28 days					Cycle ≥2 (28 days)								
Study Day	-28 to -1	1	2	3 ^a	8	15 ^a	22	1	C3D8 ^b	15					
Visit Window (days)		±2			±2	±2	±2	±2	±2	±2		±7		±7	
 Additional visit window may be allowed after discussion and agreement between investigator and sponsor. a. End of inpatient observation (PK, ECG, vital signs). b. PK/PD and ECG only.
Viral disease screen	X														
 Include HBsAg, HBcAb, and HCV antibody. In the case of apparent ongoing HBV or HCV infection, reflex serum DNA or RNA viral load testing, respectively, will be performed. See Appendix 2 for additional information.

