Visit Window (days)		±2		±2	±2		±2	±2	±2	±2		±7	±7	
a: End of inpatient observation (PK, ECG, vital signs).
 
b: This D8 visit is only applicable for Cycles 2 and 3, whereas, C3D8 is applicable for PK/PD and ECG only.

Injection site tolerability assessment		X	X	X				As clinically indicated						
 C1D1: at least 1 hour and 24 hours (±1 hr) after injection. C1D15: at least 1 hour after injection. See Section 8.2.6 for additional information
Efficacy Assessment														
Tumor response assessment	X	Performed every 8 weeks from C1D1 (±7 days) for the first 6 months, every 12 weeks (±7 days) for the next 18 months, and every 4 months thereafter.							X					
 CT/MRI scans of head, chest, abdomen, pelvis, any clinically indicated sites of disease (see Section 8.1.1).
Bone Scan or PET	X	Performed every 8 weeks from C1D1 (±7 days) for the first 6 months, every 12 weeks (±7 days) for the next 18 months, and every 4 months thereafter.							X					
 For bone metastasis (see Section 8.1.1).
Safety Assessment														
Serious and nonserious AE monitoring		↔												
 See Sections 8.2 and Section 8.3.
Clinical Safety Laboratory Assessments														
														
 See Section 8.2.4 See Appendix 2 for a list of Clinical Laboratory tests to be done.

Table 3. Study Schedule of Assessments – Part 1 With Priming

Visit Identifier Abbreviations used in this table may be found in Appendix 17	Screening	Treatment Period									EOT	4-week Follow- up	90-day Follow- up for irAEs	Notes
		Cycle 1 =28 days												
Study Day	-28 to -1	1	2 ^a	8	15	16 ^a	22	1	8 ^b	15				
 Additional visit window may be allowed after discussion and agreement between investigator and sponsor.
Visit Window (days)		±2		±2	±2		±2	±2	±2	±2		±7	±7	
a: End of inpatient observation (PK, ECG, vital signs). b: This D8 visit is only applicable for Cycles 2 and 3, whereas, C3D8 is applicable for PK/PD and ECG only.

Hematology	X	X		X	X		X	X	X (C2 only)	X	X	X		
 No need to repeat on C1D1 if screening was performed within 7 prior days. All samples will be collected prior to dosing.
Blood Chemistry	X	X		X	X		X	X	X (C2 only)		X	X		

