All participants will undergo up to 28 days of screening prior to first dose. Eligible participants will then receive study intervention for up to 2 years, or until disease progression defined by irRECIST, unacceptable toxicities, a decision by the participant (withdrawal of consent or no longer willing to participate) or investigator to discontinue treatment, or study termination. Note: If a participant is classified as having PD during an on-treatment tumor assessment, then confirmation of PD by a second scan in the absence of rapid clinical deterioration is required per irRECIST ([Appendix 13](#)).

Any additional treatment beyond 2 years shall be discussed and approved by the sponsor. After EOT, all participants will complete a 28-day post-treatment follow-up visit for AEs. All participants will be contacted by telephone approximately 90 days post treatment to assess late irAEs. Participants in Part 2 dose expansion cohorts will be contacted by telephone approximately every 3 months for survival data collection until end of trial (2 years from last participant first dose), unless otherwise notified by the sponsor.

A participant is considered to have completed the study if he/she has completed all phases of the study including the last scheduled procedure shown in the [SOA](#) including OS, if applicable. OS follow-up should not continue after end of the study ([Section 4.4](#)).

During treatment with study intervention, all cycles will be 28 days in length. Every effort should be made to administer study intervention on the planned dose and schedule. In the event of significant toxicities, dosing may be interrupted, modified, or discontinued as described in [Section 6.5](#) and [7.1](#).

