4.3.6.2. Non-Hematologic DLTs

Any treatment-related Grade ≥ 3 non-hematologic toxicity (see below for specifications applying to special circumstances):

- Hepatic toxicity:
 - Clinical events consistent with Hy's Law, ie,
 - ≥ 3 -fold elevations above the ULN of ALT or AST AND;
 - >2 x ULN elevation of serum total bilirubin without alternative explanation (eg, cholestasis or Gilbert's syndrome) AND;
 - Absence of initial findings of cholestasis (eg, elevated serum ALP) AND;
 - Absence of other reason(s) to explain the combination of increased AT and TBili, such as viral hepatitis A, B, or C; preexisting or acute liver disease; or another drug capable of causing the observed injury.
 - For participants with Grade 2 hepatic transaminase or alkaline phosphatase levels at baseline as a result of liver metastasis or bone metastasis, a hepatic transaminase or alkaline phosphatase level >10 times the ULN.
- Grade ≥ 3 fatigue lasting ≥ 5 days.
- Grade ≥ 3 nausea/vomiting or diarrhea lasting ≥ 3 days despite adequate antiemetic and other supportive care.
- Grade ≥ 3 CRS of any duration.
- Grade ≥ 3 QTcF prolongation (Repeat testing, re-evaluate by a qualified person, and correct reversible causes (such as electrolyte abnormalities or hypoxia). If, after

correction of any reversible causes, the Grade 3 QTcF prolongation persists, then the event should be considered a DLT).

- A treatment-related AE inducing a delay by >2 weeks in receiving the next scheduled cycle.
- Grade ≥ 3 anaphylaxis.
- Any Grade 5 AE (death) not clearly due to either the underlying disease or other etiologies.

In addition, irAEs that meet the following criteria will be considered as DLTs:

- Any Grade 4 irAE regardless of duration, any \geq Grade 4 colitis regardless of duration;
- Any Grade 3 or Grade 4 non-infectious pneumonitis regardless of duration;
- Any Grade 3 irAE, excluding colitis and pneumonitis, that does not start downgrading to \leq Grade 2 within 3 days after onset of the event despite maximal supportive care including systemic corticosteroids or dose not downgrade to \leq Grade 1 or baseline within 14 days;
- Any Grade 2 pneumonitis that does not resolve to \leq Grade 1 within 3 days of the initiation of maximal supportive care.

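### With priming, the DLT window closes on the Day 43 (C2D15) laboratory results, but Table 3 schedules no blood chemistry at that visit, so a silent chemistry-based DLT arising after Day 36 can be missed or seen too late

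*Protocol*

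**What the plan says.** Protocol Section 4.3.6 gives the primed window by example. For a single prime given two weeks ahead of full dosing, it states that "the DLT evaluation period will be 42 days (14 days plus 28 days"). It then names the reading that closes this window: "including laboratory results obtained on the morning of Day 43 (C2D15"). The closing results are not limited to any one panel.

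The schedule for these participants is Table 3 in Section 1.3.2. Without the empty cells, its two main laboratory rows read:

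- "Hematology X X X X X X X (C2 only) X X X"
- "Blood Chemistry X X X X X X X (C2 only) X X"

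After the Day 8 entry, hematology has three marks (Day 15, end of treatment, 4-week follow-up). Chemistry has two, in the end-of-treatment and 4-week columns. The Cycle 2 and later Day 15 cell is the one left empty. In Table 1, the schedule without priming, the row "Blood chemistry X X X X X X X X X X" includes a mark at that visit.

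Section 4.3.6.2 defines DLTs that depend on chemistry. The Hy's Law criterion requires "≥ 3 -fold elevations above the ULN of ALT or AST AND" a bilirubin rise: more than twice the ULN "elevation of serum total bilirubin without alternative explanation". Another criterion is a transaminase or alkaline phosphatase level above 10 times the ULN in participants with Grade 2 baseline values due to metastasis. Other treatment-related Grade 3 or higher non-hematologic toxicity also counts, with listed exceptions.

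**The concern.** The DLT rate is a primary estimand for Part 1, and the definition of the window and the schedule that supplies its data disagree about the last sample. A site working from Section 4.3.6 could draw chemistry on Day 43, while a site working from Table 3 would not. Ascertainment could then differ between sites.

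It could also differ between regimens. Without priming, the closing reading is Day 29 (C2D1), where Table 1 does schedule chemistry. Under Section 9.3.2 the unprimed data supply the prior for the primed model, so the two sets of DLT counts should be collected to the same standard.

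Cohorts are about 3 participants. One unrecorded event turns 1 of 3 into 0 of 3. Under Section 4.3.5 an observed DLT also lowers the maximum dose increment from 200% to 100%, so a single missed event could affect both the model and the permitted step.

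**Working it through.** **Inputs.** Cycle length: "During treatment with study intervention, all cycles will be 28 days in length" (Section 4.1). Primed window: 14 + 28 days (Section 4.3.6). Chemistry visits in Table 3: screening, C1D1, C1D8, C1D15, C1D22, Day 1 of each later cycle, Day 8 of Cycle 2 only, end of treatment and 4-week follow-up. Visit window at C2D8: ±2 days.

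**Reproducing the plan's own figures.** Study day = 28 × (cycle − 1) + cycle day.

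- C2D15 = 28 + 15 = 43, as Section 4.3.6 states.
- Window = 14 + 28 = 42 days, as stated.

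**Where the chemistry falls.**

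- C2D1 = 28 + 1 = Day 29 (second full dose).
- C2D8 = 28 + 8 = Day 36 (last scheduled chemistry in the window).
- C3D1 = 56 + 1 = Day 57 (next scheduled chemistry for a participant still on treatment).

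**Size of the gap.**

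- Days without a later chemistry inside the window: 42 − 36 = 6 (Days 37 to 42). 6/42 = 14%.
- These are 37 − 29 = 8 to 42 − 29 = 13 days after the second full dose.
- Interval from C2D8 to Day 43: 43 − 36 = 7 days. With the visit on Day 38 or Day 34 it is 5 or 9 days.
- From Day 36 to C3D1: 57 − 36 = 21 days. From Day 43 to C3D1: 57 − 43 = 14 days.

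**Does other text require the sample?**

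- Section 8.2.4 ties laboratory timing to the schedule of activities. Unscheduled tests are allowed, not required.
- Section 6.5.2 sets laboratory conditions for re-treatment after a toxicity interruption or at the start of a cycle. A routine C2D15 dose is neither, and the values it names are neutrophils and platelets.
- Evaluability in Section 4.3.6 asks for the planned doses and the scheduled safety assessments. A participant with no chemistry after Day 36 who followed Table 3 meets it.

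So no text outside Section 4.3.6 secures the chemistry that would close the window.

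**The case against.** The strongest reply is that Section 4.3.6 already calls for Day 43 laboratory results without limiting them to hematology, so the blank in Table 3 is a slip and sites will draw chemistry anyway. It probably is a slip, since no reason for the omission is given. But sites work from the schedule, Section 8.2.4 points them to it, and the two places still conflict.

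Several safeguards narrow what could be lost:

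- Section 4.3.7 brings late-onset toxicities that meet the DLT definition into the evaluation of the MTD and the expansion dose, and the Dose Level Review Committee (Section 4.3.8) considers all relevant data.
- An elevation already evident by Day 36 leads to closer monitoring under Appendix 6 and the hepatic table in Section 10.3.5.
- Section 4.3.6.3 excludes isolated Grade 3 laboratory abnormalities without sequelae that are corrected within 72 hours.
- C2D15 is an attended visit, and a symptomatic participant could have an unscheduled test.

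All of this stands. What remains is a new, clinically silent event after Day 36. It may resolve unseen, or appear only on Day 57, when an escalation decision may already have been taken and its onset can no longer be placed inside or outside the window.

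A last caution concerns the evidence. It is one empty cell, and in a text copy of Table 3 other rows (weight, lipase and amylase) look displaced by a column. The chemistry row does not: it has as many cells as the hematology row, and its Cycle 2 entry sits under Day 8 in both. A single lost mark cannot be ruled out without looking at the printed page.

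**Conclusion.** The conflict between Section 4.3.6 and Table 3 is real and bears on a primary endpoint. Its size is 6 of 42 days (14%) without closing scheduled chemistry, for single-prime participants only. This rests on the Table 3 cell being blank as printed, C2D8 held on its nominal day, and treatment continuing past C2D15 so that the end-of-treatment sample does not intervene.

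Three stronger readings are tempting but not supported:

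- A reader might infer that any chemistry DLT after Day 36 is certain to go unseen and be recorded as no DLT. Late-toxicity review, intensified monitoring of known elevations and optional testing mean only that it can be missed or seen late.
- A reader might divide the 7-day interval by 42 and report 17%. Day 43 is the reading after the window, not one of its 42 days. Nor is 14% a share of DLTs lost: the documents give no basis for estimating how many would be missed or whether a model decision would change.
- A reader might extend the point to chemistry frequency in later cycles. That lies outside the DLT window and does not affect this endpoint.

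Hematology is covered at C2D15, and the unprimed schedule, where the trial starts, has its closing chemistry. The gap arises only if a primed cohort is opened, which Section 4.1 makes conditional.

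**What to change.** Before any primed cohort opens, reconcile Table 3 with Section 4.3.6 and with Table 1 so that the Day 43 (C2D15) laboratory results that close the DLT window include blood chemistry. The simplest form is a chemistry mark in Table 3 at Day 15, at least for Cycle 2, using the blood draw already scheduled there for hematology. A phrase in Section 4.3.6 naming the panels that make up the closing results would stop the two places drifting apart again. This moves the last scheduled chemistry from Day 36 to Day 43 and covers Days 37 to 42. The cost is one schedule cell and one extra tube per participant, with no additional visit.
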